***PRGF VS CGF in management of
labial dehiscence around immediate
implants (Comparative study)***

Clinical trial registration: NCT05595772

Document Date: July 30, 2022

Introduction and Review

With the increase in esthetic demand, dental implants have become an indispensable part of modern dental practice. However, with the increasing practice of dental implants; the esthetic outcome is considered as important as the functional and biological outcome. **(Haas et al., 2002)**

Immediate implants have been evolved as the first treatment option in cases of the failed tooth to decrease the time of treatment plan. Immediate implantation at the time of tooth extraction has been associated with significantly higher patient satisfaction (95%) compared to early (84%) or delayed (80%) implant placement. **(Hof M. et al., 2015)**

To obtain an effective esthetic outcome with a single implant-supported restoration in the anterior region, it is crucial to preserve and maintain intact the bone anatomy, as well as the overlying soft tissues. The challenge in treatment is when the labial bone plate presents with a dehiscence type defect stemming from etiologies such as chronic inflammation from a mid-facial vertical fracture affecting the periodontal attachment or severe trauma and chronic infection. **(Sarnachiaro GO et al., 2016) (Fürhauser, R. et al., 2017)**

The compromised esthetic result is anticipated when a 1- to 2-mm vertical deficiency in soft tissue is noted. For defects ≥ 2 mm, soft tissue augmentation should be considered before implant insertion. The keratinized gingival (KG) width on the mid-buccal side of the socket: ≥ 2 , 1 to 2, and <1 mm were defined as adequate, compromised, and deficient, respectively. **(Juodzbalsys et al., 2008)**

The extraction sockets were divided into four groups: Class I, intact soft tissue wall and bone walls; Class II, intact soft tissue wall with the destruction of at least one bone wall; Class III, the recession of all soft tissue walls by ≤ 5 mm; and Class IV, the recession of at least one soft tissue wall by >5 mm **(Cheng et al., 2021)**

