Platelets have been identified as a manufacturer of high quantity of growth factors, such as Platelet-Derived Growth Factor (PDGF), Transforming Growth Factor-B1 (TGF), TGF-B2, Fibroblast Growth Factor (FGF), Vascular Endothelial Growth Factor (VEGF), Insulin-like Growth Factor (IGF) that invigorating cellular proliferation, matrix remodeling and neo-angiogenesis **(Pakyari, M et al., 2013)**

Four major categories of products can be simply defined, based on their leukocyte content and fibrin architecture: pure platelet-rich plasma, such as Cell Separator PRP or Anitua' PRGF; leukocyte- and platelet-rich plasma (L-PRP), such as PCCS or Ace PRP; pure platelet-rich fibrin (P-PRF), such as Fibrinet PRFM; and leukocyte- and platelet-rich fibrin (L-PRF), such as Choukroun's PRF. **(Chou T-M et al., 2020)**

Plasma rich in growth factors (PRGF), a subtype of P-PRP (pure platelet-rich plasma), is a supernatant enriched in plasma and platelet-derived morphogens, proteins, and growth factors. PRGF represents a complex pool of active mediators that may stimulate and accelerate tissue regeneration, which is generally safe to use and economical to obtain. Autologous PRGF has been approved for clinical use by the European Community and the U.S. Food and Drug Administration (**Anitua et al., 2014**) (**Dohan Ehrenfest et al., 2009**)

The drawback of PRP is its complex preparation process: several procedures are needed to segregate it and it has to be activated by thrombin and calcium chloride. (**Chen, X et al., 2018**)

CGF (concentrated growth factor), the third-generation platelet concentrate presented by Sacco in 2006 carries more growth factors and has a firmer fibrin structure than first-generation PRP and second-generation PRF (platelet-rich fibrin) . Sacco's membrane (CGF) shows a complex three-dimensional architecture which makes it a biomaterial rich in fibrin platelets, leukocytes, and growth factors - very satisfactory both for patient and operator (**Dohan et al., 2006**) (**Chen, X et al., 2018**)

In comparison with previous generations of platelet enrichment, the preparation of CGF membranes does not need additional reagents to generate platelet activation or fibrin polymerization and is less likely to develop immune responses or cross infections (**W. M. Talaat et al., 2018**)

Aim of the study

- Assess the effectiveness of PRGF and CGF in the management of buccal dehiscence and marginal bone level around the immediate implant.

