- Compare the effectiveness of PRGF Vs CGF.

Patients and Methods

Patient selection

this study will be conducted on 20 patients indicated for immediate implant placement in the maxillary anterior region. After approval from the ethical committee, the entire patients will be recruited from the outpatients' clinic of the Oral Medicine, Oral Diagnosis, and Periodontology Department. Faculty of Dentistry, Minia University.

Inclusion criteria:

1. Selected patients of both sexes are 20-40 years old.
2. Patients are systemically healthy based on questionnaire dental modification of Cornell index.
3. Gingival health according to the new classification system (2017)
4. The recipient site of the implant is free from any pathological conditions.
5. Class II extraction socket according to Chang's classification system
6. Adequate interocclusal space to accommodate the available restorative components.
7. Adequate native/apical bone to achieve primary implant stability.

Exclusion criteria:

1. Pregnant female.
2. Parafunctional habits such as bruxism and clenching Patients suffering from periodontitis.
3. Smokers.

Ethical regulation and Informed consents

All patients will undergo an immediate implant placement and the complete treatment plan will be explained to all patients including detailed steps, risks, and expected results. Verbal and written informed consent will be obtained from all patients before the commencement of the study. All steps will be examined and approved by the appropriate ethics committee and have therefore been performed following the ethical standards laid down in the Declaration of Helsinki and the research ethics committee of the Faculty of Dentistry, Minia University.

Pre-surgical phase

1. All selected patients will be screened by comprehensive periodontal examination and full periodontal charts will be obtained. A preoperative cone-beam computed tomography (CBCT) will be performed for each patient who met the inclusion criteria before the surgery to determine bone height and width and decide the implant length and diameter to be placed and to evaluate the underlying bone condition.

Randomization

The study will use simple randomization to allocate patients into 2 groups, each group will be included 10 patients.

Group A: (concentrated growth factor group)

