ten patients indicated for immediate implant in the maxillary anterior region (class II socket), will be a candidate for immediate implant placement with CGF combined with xenogeneic bone graft

Protocol for CGF preparation:

10 ml venous blood samples will be drawn from the patients and placed in a centrifuge tube without anticoagulants. Then the tubes will be placed in the centrifugation device in an opposing balanced manner and rotated in four sequential steps. The first step at 735 g ($2249 \approx 2200$) for 2 min., the second one at 580 g ($1998 \approx 2000$) for 4 min., the third one at 735 g ($2249 \approx 2200$) for 4 min. and the fourth one at 905 g ($2495 \approx 2500$) for 3 min. The result was a clot that was collected using a straight tweezer and ready to be used

Group B: (platelet-rich in growth factor group)

Ten patients who indicated immediate implant in the maxillary anterior region (class I or class II socket), will be a candidate for immediate implant placement with PRGF combined with xenogeneic bone graft.

Protocol for PRGF preparation:

30 ml venous blood will be collected from the patient then deposited in 5 mL tubes containing sodium citrate anticoagulant. Then the tubes will be centrifuged at 580 G (2270 rpm) for 8 minutes at room temperature. After centrifugation, the blood sample will be layered into the following four distinctive layers:

- 1) 0.5 mL Plasma poor in growth factors (PPGFs) = F1 in the uppermost part of the tube
- 2) 0.5 mL Plasma with growth factors (PGFs) = F2
- 3) 0.5 mL (PRGF) = F3 located immediately above the red blood cell portion in the tube
- 4) Red blood cell concentrate layer

From all tubes, The 500 μ L PPGF will be eliminated and the PRGF will be separated with 500 μ L pipettes and transported to an independent dish then activated using 50 μ L of 10% calcium chloride for every 1 ml of preparation and mixed with xenogenic bone graft then it will be incubated for 40 minutes in 37°C to produce easy to handle gelatinous layer (PRGF) fibrin mixed with the xenogenic bone.

Surgical Phase

1. The surgical site will be prepared by scrubbing the surgical site using Betadine: Povidone-iodine, 7.5% (0.75% available iodine) the Nile Comp. for Pharmaceuticals and Chemical Industries, Alexandria, Egypt
2. Nerve block or infiltration anesthesia will be administrated Articaine (4%) with epinephrine (1:100,000 or 1:200,000)

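### Group B's socket description admits class I, contradicting inclusion criterion 5 and Group A; if it is applied, the PRGF–CGF comparison is confounded by baseline defect

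*Combined protocol and SAP*

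**What the plan says.** Socket class appears in three places in the combined protocol and SAP that bear on who enters the trial.

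- Inclusion criteria, item 5, applies to all patients: "Class II extraction socket according to" a named classification system. Class II is the only class listed.
- The Group A (CGF) description under Randomization: "ten patients indicated for immediate implant in the maxillary anterior region (class II socket".
- The Group B (PRGF) description: "Ten patients who indicated immediate implant in the maxillary anterior region (class I or class II socket".

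The Introduction defines the two classes: "Class I, intact soft tissue wall and bone walls", and "Class II, intact soft tissue wall with the destruction of at least one bone wall". It is the only numbered socket scheme in the document, and I take it to be the one that criterion 5 means.

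The first aim is "Assess the effectiveness of PRGF and CGF in the management of buccal dehiscence and marginal bone level around the immediate implant"; the second is "Compare the effectiveness of PRGF Vs CGF". Allocation is by simple randomisation, 10 patients per group and 20 in total. No stratification by socket class is stated. The Statistical analysis section is one general sentence that names no test, no significance level and no covariate.

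**The concern.** Randomisation makes two arms comparable only if every randomised patient could have gone to either arm. The Group B description breaks that condition: read literally, a class I patient is acceptable for PRGF and not for CGF. Such a patient would have to be placed in PRGF without randomisation, or randomised and then dropped if the draw was CGF. Either way, treatment arm would depend on the state of the socket before treatment.

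The imbalance would be in the feature the trial sets out to treat, since a class I socket has no bone wall missing. A difference between the arms at 9 months could then reflect which sockets were treated rather than which concentrate was used. Randomisation would not remove it, and nothing in the analysis text would adjust for it. This is the trial's only between-arm comparison, and with 10 per arm a few such patients carry weight.

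**Working it through.** **Step 1: compare the texts.**

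| Place | Class I | Class II |
|---|---|---|
| Inclusion criterion 5 (whole trial) | no | yes |
| Group A, CGF | no | yes |
| Group B, PRGF | yes | yes |

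The first two rows agree. The third conflicts with both, and the document does not say which text governs.

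**Step 2: inputs for size.** The only usable figures in the document are 10 per group and 20 in total (10 + 10 = 20). It gives no power calculation, SD, expected effect or significance level, so there is no sponsor figure to reproduce beyond that sum. The rest is assumed: k class I patients among the 10 in Group B; a mean difference of D SD between class I and class II sockets at 9 months; no true PRGF–CGF difference; equal SD; a two-sample t-test at two-sided 5%.

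**Step 3: bias.** Bias = (k/10) × D, in SD units.

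- k = 0: 0 for any D.
- k = 1, D = 2: 0.1 × 2 = 0.2.
- k = 3: 0.3 × 0.5 = 0.15; 0.3 × 1 = 0.3; 0.3 × 2 = 0.6.
- k = 5: 0.5 × 0.5 = 0.25; 0.5 × 1 = 0.5; 0.5 × 2 = 1.0.

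**Step 4: false-positive rate.** Under the same assumptions, both arms were drawn from a standard normal distribution, k Group B values were shifted by D, and p-values below 0.05 were counted over 200,000 simulated trials.

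| k of 10 | D = 0.5 | D = 1 | D = 2 |
|---|---|---|---|
| 0 | 5% | 5% | 5% |
| 1 | 5% | 5% | 5% |
| 3 | 6% | 8% | 14% |
| 5 | 8% | 15% | 37% |

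A single class I patient shifts the estimate but does not visibly raise the error rate.

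**Step 5: scale.** With 10 per arm, the difference detectable with 80% power is (1.960 + 0.842) × √(2/10) = 1.25 SD by the normal approximation, or 1.32 SD by the t-test. A bias of 0.5 SD is 0.5/1.32 = 38% of that; a bias of 1.0 SD is 1.0/1.32 = 76%.

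**Step 6: direction.** The Radiographic evaluation section lists bone density and marginal bone level by CBCT at 9 months. It does not say whether these are analysed as levels or as changes from the preoperative scan. For an absolute marginal bone level, sockets that start with intact walls would plausibly do better, which favours PRGF. For bone gain or defect fill, a class I socket has no defect to fill, so the effect could be nil or run against PRGF. For density the document gives no basis for a direction.

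**The case against.** The strongest reply is that this is a drafting slip with no consequence. The protocol has one inclusion list for the whole trial, limited to class II. It then describes a preoperative CBCT for patients who met that list, and then randomisation. Followed in that order, no class I patient reaches allocation, k is 0 and the bias is 0. The title and the first aim, both about dehiscence, fit this reading.

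That argument stands as far as it goes. A reader might infer from the Group B text that patients will be sorted into arms by socket class and that the comparison is confounded as designed. The documents do not support that: nothing says class I patients will in fact be enrolled, and nothing describes allocation by socket class.

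A reader might also infer that any class I patient must flatter PRGF. That does not follow either, because the outcomes are not defined as levels or changes and the direction differs between them.

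A third fair point is that the class I share and the size of D are not in the documents, so an honest range has to start at no inflation.

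The reply does not remove the contradiction. Nothing states that criterion 5 overrides the Group B text, so a site reading the arm descriptions could enrol class I patients to PRGF in good faith.

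**Conclusion.** The contradiction is certain, and the Group B description is wrong as written. The confounding is conditional: it arises only if the Group B text is applied in place of criterion 5. In that case baseline defect is tied to treatment arm and the plan states nothing to correct it. Under the assumptions in the working (0 to 5 of 10 class I, D from 0.5 to 2 SD), the bias runs from 0 to 1.0 SD and the false-positive rate from the nominal 5% to about 37%. These figures illustrate what could happen and do not predict what will. A tilt towards PRGF is probable only for absolute 9-month marginal bone level. The point should be settled before the comparison is relied on, because it concerns who is eligible for each arm.

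**What to change.** Reconcile the three texts by deleting the class I option from the Group B description. One class II criterion, consistent with criterion 5, Group A, the title and the aim, then applies to every patient. State that socket class is confirmed and recorded before randomisation and that no arm has its own eligibility rule.

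If any class I patient has already been enrolled, report socket class by arm and make the class II patients the primary comparison.

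The amendment is one line and leaves the planned 20 patients unchanged. Recruitment to the trial as a whole may be slightly slower if class I patients were being counted. Setting enrolled class I patients aside costs precision. With three of them in Group B the comparison is 10 against 7, and the standard error of the difference rises from √(1/10 + 1/10) = 0.447 SD to √(1/10 + 1/7) = 0.493 SD, about 10%. With five it is 10 against 5: √(1/10 + 1/5) = 0.548 SD, about 22% more.

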3. Atraumatic extraction of the tooth or remaining root using periotome, then sequential implant drilling accompanied by copious irrigation will be carried out. then cover screw attached to the implant top by the aid of its driver
4. A sample of venous blood will be withdrawn from the patient and centrifuged without delay according to the preparation protocol of each group.
5. Then the membrane loaded with the bone graft will be applied and condensed around the dental implant filling the gap between the fixture and the walls of the socket.
6. Finally, Tension-free Closure of the wound was achieved using 4/0 vicryl sutures.

Postoperative instructions

1. Routine verbal and written postoperative instructions for periodontal surgery will be given to all patients including ice compression on the surgical site during the first 4 h, a liquid and/or soft food diet for 3 days.
2. As with all surgical procedures, patients will be informed to contact our clinic if any problems will be developed during the postoperative period.
3. The postoperative medications prescribed will be (Amoxicillin+ clavulanic acid*625mg for 7 days) every 8 h or clindamycin** 300 g every 12 h for 7 days for patients allergic to penicillin, and (Ibuprofen*** 600 mg every 12 h for 5 days).
4. The sutures will remain in situ for 2 weeks.

Clinical assessment:

All patients included in the present study will be followed carefully and monitored to motivate the patient for oral hygiene instructions and maintenance of good oral hygiene.

*Augmentin®, GlaxoSmithKline

** Dalacin C®, Pfizer

*** Brufen®, Abbott

Radiographic evaluation

A periapical film with the paralleling technique will be used immediately after the implant placement

And after 9 months CBCT imaging will be used to evaluate:

1- Bony density

2- Marginal bone level.

Statistical analysis:

-All data will be tabulated and analyzed by statistical method.

References

- Araújo, M. G., & Lindhe, J. (2005). Dimensional ridge alterations following tooth extraction. An experimental study in the dog. *Journal of clinical periodontology*, 32(2), 212–218.

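### As the surgical steps are numbered, blood is drawn only after the cover screw is fitted, so on stated times alone the open socket waits at least 13 min for graft with CGF and at least 48 min with PRGF

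*Combined protocol and SAP*

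**What the plan says.** The Surgical Phase is one numbered list for both groups.

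- Step 3 covers extraction and drilling and ends "then cover screw attached to the implant top by the aid of its driver".
- Step 4: "A sample of venous blood will be withdrawn from the patient and centrifuged without delay according to the preparation protocol of each group".
- Step 5: "Then the membrane loaded with the bone graft will be applied and condensed around the dental implant filling the gap" between implant and socket walls.
- Step 6: "Finally, Tension-free Closure of the wound was achieved using 4/0 vicryl sutures".

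The preparation times are given earlier, under each group. For CGF, 10 ml of blood is "placed in a centrifuge tube without anticoagulants". It is spun in four consecutive runs lasting 2, 4, 4 and 3 min, after which the clot can be used. For PRGF, 30 ml of blood is collected into citrated tubes and spun "for 8 minutes at room temperature". The PRGF layer is then pipetted off, activated with calcium chloride, "mixed with xenogenic bone graft then it will be incubated for 40 minutes" at 37°C.

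No other section places the blood draw before surgery, sets a common waiting time, or asks for the interval between implant and graft to be recorded.

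**The concern.** The second aim is to compare PRGF with CGF. Both arms receive a xenogeneic graft, so the platelet product is the intended difference. If staff follow the numbering, a second difference comes with it: how long the implant sits in an open, ungrafted socket. That interval follows the allocated arm, and no clock times are kept, so its size could not be described afterwards. Recording it under the present order would help only in part. The wait would still largely coincide with the arm, and 20 patients could not reliably separate the two.

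Two things are at stake. One is interpretation: a difference between arms would belong to the product together with its wait, and attribution to the material alone would be less clear. The other does not depend on the outcomes. Every patient, and PRGF patients most, has open-wound time under local anaesthesia that drawing the blood sooner would largely avoid.

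**Working it through.** The plan states no total preparation time or graft delay, so there is no figure to reproduce. The check has two parts: the order of steps and the sum of the stated times.

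**Order.** Step 3 ends with the cover screw, step 4 draws and spins the blood, step 5 opens with a word of sequence, and step 6 opens with a word of conclusion. Implant insertion is not written. It is inferred from a cover screw being fitted to the top of the implant. The instruction in step 4 to avoid delay concerns the time from draw to spin, not from implant to graft.

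**Stated times** (from the two preparation protocols).

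- CGF: 2 + 4 + 4 + 3 = 13 min.
- PRGF: 8 + 40 = 48 min.
- Difference: 48 − 13 = 35 min.

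In the PRGF arm the graft is mixed in before incubation starts, so grafting with that material cannot begin during the 40 min.

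**Unwritten handling.** The draw, tube loading, pipetting, activation and mixing have no stated duration, so 13 and 48 min are minimums. With handling times hC (CGF) and hP (PRGF):

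- Wait with CGF = 13 + hC; wait with PRGF = 48 + hP.
- Difference = 35 + hP − hC.

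Assume handling of 0 to 15 min in each arm; this range is not in the document.

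| hC (min) | hP (min) | CGF wait | PRGF wait | Difference |
|---|---|---|---|---|
| 0 | 0 | 13 | 48 | 35 |
| 15 | 15 | 28 | 63 | 35 |
| 15 | 0 | 28 | 48 | 20 |
| 0 | 15 | 13 | 63 | 50 |

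The difference disappears only if hC − hP = 35, that is, if CGF handling takes 35 min longer than PRGF handling. The written PRGF steps look longer, not shorter: 30 ml in 5 ml tubes is 30 / 5 = 6 tubes if filled, each to be pipetted, followed by activation and mixing. Loading CGF with graft is not described or timed.

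**Source of the wait and of the gap.** Step order is the same in both arms. It explains why there is a wait at all but cannot by itself create a difference. On spin time alone PRGF is shorter by 13 − 8 = 5 min. The 40 min incubation turns that into a PRGF wait longer by 40 − 5 = 35 min.

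**The case against.** The strongest reply is that the list is weak evidence of real timing. It leaves out implant insertion, changes tense in step 6, and does not say how CGF is combined with the graft. Step 4 has no linking word of its own, so blood prepared alongside step 3 would also fit the wording of steps 5 and 6. This stands in part. The numbered order is still the natural reading, and nothing elsewhere contradicts it, but if it is only loose drafting, writing down the real order settles the matter.

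A second reply is that preparation is part of each treatment. The aim speaks of effectiveness, and the introduction already names complex preparation as a drawback of platelet-rich plasma, the family to which PRGF belongs. This also stands: randomisation supports a fair comparison of the two procedures as delivered. Preparation time does belong to the product, but spending it with the socket open is a choice of sequence.

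A third reply is that moving the draw has a price, because the arm would be known before extraction. That is true. However, the plan nowhere hides the arm from the surgeon, so no stated protection is lost.

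Three stronger readings are tempting, and the document supports none of them.

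- A reader might infer that the delay biases the 9-month result or invalidates the comparison. The document does not say how open-socket time affects bone density or marginal bone level.
- A reader might blame the 35 min gap on step order alone. The gap comes from the preparation times.
- A reader might take 35 min as the least possible gap. It is a difference of two minimums and could be smaller or larger.

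**Conclusion.** The point holds as a minor one. Followed as written, the plan leaves the open socket waiting at least 13 min with CGF and at least 48 min with PRGF. The stated times differ by 35 min, or by 20 to 50 min under the assumed handling range. The wait exists in both arms because step 4 follows step 3; its difference between arms comes chiefly from the PRGF incubation.

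This rests on reading the numbered list as a sequence and on the implant being in place when its cover screw is fitted. Any effect on the 9-month outcomes is unknown in size and direction, and none can be computed from the document. What can be said is that the order adds avoidable open-wound time, ties implant-to-graft delay to the arm, and so makes it harder to credit a difference to the material alone.

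**What to change.** Move the blood draw out of step 4 to before extraction in both arms.

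- **CGF:** draw shortly before extraction and spin at once, since the blood has no anticoagulant.
- **PRGF:** count back from the expected cover-screw time and draw at least 48 min plus handling before it, so that the graft-loaded material is ready when the cover screw is fitted.
- **Both arms:** record the clock times of implant seating and graft placement, and report the interval by arm. A third time, material ready, is optional and would show how long the product was held.

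For illustration, suppose step 3 takes 20 to 45 min (an assumption) and leave handling aside. The PRGF draw then falls between 48 − 20 = 28 and 48 − 45 = 3 min before extraction. CGF drawn as extraction begins would be held for 20 − 13 = 7 to 45 − 13 = 32 min.

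The cost is one step moved, a few lines of wording and two clock times per patient. There are four downsides:

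- Prepared material may be held, for longer if surgery overruns. The document gives no limit, so the sponsor should confirm an acceptable time for each product.
- The amount of graft mixed with PRGF is set from the preoperative CBCT, before the defect is seen directly.
- Blood is occasionally drawn needlessly, if the socket proves unsuitable or the implant cannot be placed.
- The arm is known before extraction.

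If blood is in fact already drawn before extraction, correcting the step order in the text is enough.

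### Postoperative instructions, item 3: the antibiotic entry for penicillin-allergic patients is in grams beside two milligram entries and cannot be followed as written (minor unit error)

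*Combined protocol and SAP*

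**What the plan says.** The combined protocol and SAP sets out the drugs to be given after surgery in one sentence, Postoperative instructions, item 3. It opens "The postoperative medications prescribed will be", so it is an instruction and not background. It has three entries:

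- First-line antibiotic: "Amoxicillin+ clavulanic acid*625mg for 7 days) every 8 h".
- Clindamycin as the alternative: "300 g every 12 h for 7 days for patients allergic to penicillin".
- Ibuprofen: "600 mg every 12 h for 5 days".

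The only other trace of clindamycin is a footnote in the Clinical assessment section, which gives a brand and a manufacturer but no strength.

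Under Patient selection, "this study will be conducted on 20 patients indicated for immediate implant placement". The exclusion criteria cover pregnancy, parafunctional habits, periodontitis and smoking. Penicillin allergy is not among them, and item 3 itself provides for patients who have it.

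**The concern.** One of three entries in a prescribing sentence is in grams and the other two are in milligrams. A difference in unit is not an error in itself, since different drugs may properly be written in different units. What makes this one an error is the amount that results when the entry is read as it stands.

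The stake is narrow but concerns patients directly. For a participant allergic to penicillin this is the only antibiotic instruction the protocol gives, and it cannot be carried out as written.

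**Working it through.** The protocol derives no figure here, so there is no calculation of its own to reproduce. The check is a unit conversion and a count of administrations.

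**Inputs, all from item 3**

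- First-line antibiotic: 625 mg, 8-hourly, 7 days.
- Clindamycin: 300 g, 12-hourly, 7 days.
- Ibuprofen: 600 mg, 12-hourly, 5 days.

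**Step 1. Common unit.** With 1 g = 1,000 mg, 300 g × 1,000 = 300,000 mg per administration.

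**Step 2. Ratio to the neighbouring entries.**

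- 300,000 / 625 = 480.
- 300,000 / 600 = 500.

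The units differ by a factor of 1,000, but the written amounts differ by 480 and 500. These ratios compare masses of different drugs. They show scale and say nothing about relative potency or exposure.

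**Step 3. Whole course as written.**

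| Entry | Administrations | Total as written |
|---|---|---|
| First-line antibiotic | (24/8) × 7 = 21 | 21 × 625 mg = 13,125 mg = 13.125 g |
| Clindamycin | (24/12) × 7 = 14 | 14 × 300 g = 4,200 g |
| Ibuprofen | (24/12) × 5 = 10 | 10 × 600 mg = 6,000 mg = 6 g |

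A week's course of 4,200 g (4.2 kg) cannot be what was meant.

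**Step 4. Does another part of the document settle it?** No. The brand footnote carries no strength, and no other section restates, corrects or explains the entry.

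**Step 5. How many patients could it reach?** The document gives no frequency of penicillin allergy. The possible range is therefore 0 to 20 of the 20 planned patients, with no basis in the text for a narrower one.

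**Step 6. Could the text extraction have lost a character?** This cannot be ruled out, because the text was machine-read from a PDF. However, the milligram symbol survives twice in the same sentence, and the microlitre symbol survives under Protocol for PRGF preparation, though with a stray space. A reading fault is unlikely, but the source page should be checked.

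**The case against.** The strongest reply is that the slip reveals itself. Nobody could prescribe, dispense or take the literal amount, and the dangerous unit errors are the plausible ones that pass unnoticed. The product is named, so its labelling can be consulted. This largely stands, and it is why the point is minor. It does not remove the point, because noticing that the entry is impossible does not show what the protocol intended.

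A reader might infer more than the document supports:

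- **That staff would have to guess, or that co-medication would become non-uniform.** Neither is shown. Prescribers querying the entry against a named product may all resolve it in the same way, and the antibiotic already differs by allergy status by design.
- **That 4,200 g measures harm or likely exposure.** It shows only that the text is impossible as it stands.
- **That the trial's results are at risk.** Nothing links this entry to bone density or marginal bone level, the two measures listed under Radiographic evaluation.
- **That the other two entries are also suspect.** No fault has been identified in either.
- **That the intended amount is obvious from the neighbouring units.** The document states no strength for this drug, and the choice belongs to the sponsor and the prescriber.

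**Conclusion.** The point holds as a minor but real unit error in operative prescribing text. As written, the entry is 300,000 mg per administration, 480 and 500 times the figures beside it, and 4,200 g over 14 administrations. It cannot be followed, and no other part of the document resolves it.

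The practical risk is limited because a prescriber or pharmacist would very probably query the amount. That is a judgement, not something the document establishes. Design, endpoints and analysis are unaffected. The conclusion also assumes that the source page reads as the extracted text does.

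**What to change.** 1. Check item 3 on the source page. If the unit there differs from the extracted text and is consistent with the rest of the sentence, nothing further is needed.
2. If it reads the same, the sponsor and the responsible prescriber should reconcile the unit with the rest of the sentence and with the labelling of the named product.
3. Issue a corrected item 3 before any penicillin-allergic patient is treated.

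This review does not propose a dose. The cost is a one-line correction notified to the ethics committee. Sample size, allocation, assessments and analysis stay as they are.
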